## 2.2.2 Clinical Experience

CEGF816X2101 is the first-in-human Phase I/II study of single-agent oral EGF816, and is currently ongoing. As of the data cut-off date (18-Dec-2015), 148 patients have been treated with EGF816 capsules or tablets at seven dose levels: 75 mg q.d. (N=7), 100 mg q.d. (N=29), 150 mg q.d. (N=64), 200 mg q.d. (N=8), 225 mg q.d. (N=24), 300 mg q.d. (N=5) and 350 mg q.d. (N=11). Eighty-four patients (56.8%) were still receiving treatment and 64 patients (43.2%) had discontinued treatment. Of these 64 patients, 53 (35.8%) discontinued treatment due to progressive disease, three (2.0%) discontinued treatment due to AEs, and 3 (2.0%) discontinued treatment due to death. Of the three patients who discontinued treatment due to

AE, one patient at the 350 mg q.d. reported Grade 3 maculopapular rash, one patient at the 150 mg daily dose reported Grade 3 interstitial lung disease, and one patient at the 300 mg daily dose reported Grade 3 pulmonary oedema. Of the three patients who discontinued treatment due to death, one patient died due to sepsis (considered not related to study treatment), one patient died due to hepatitis B virus (HBV) reactivation (considered related to study treatment), and one patient died due to pneumonia (considered not related to study treatment).

As of 18-Dec-2015, dose-limiting toxicities (DLT) were reported in five patients: one patient at the dose level of 150 mg capsule reported Grade 3 maculopapular rash that resulted in temporary treatment interruption, one patient at the dose level of 225 mg capsule reported Grade 3 maculopapular rash that resulted in temporary treatment interruption, one patient at the dose level of 350 mg capsule reported Grade 3 acute kidney failure and Grade 3 maculopapular rash that resulted in temporary treatment at the dose level of 350 mg capsule reported Grade 3 acute kidney failure and Grade 3 maculopapular rash that resulted in temporary treatment at the dose level of 350 mg capsule reported Grade 3 maculopapular rash that resulted in permanent discontinuation of treatment, and one patient at the dose level of 350 mg capsule reported. Grade 3 enteritis and Grade 3 dehydration that resulted in temporary treatment interruption.

As of the data cutoff date of 18-Dec-2015, 142 patients (95.9%) who were treated with EGF816 capsules or tablets experienced at least one AE of any grade, regardless of relationship to the study drug. The most frequent AEs (all CTCAE grades, >10% of patients) regardless of study drug relationship at the seven dose levels specified below were rash (group term) (56.1%), diarrhea (41.9%), maculopapular rash , pruritus (36.5%), fatigue (27.0%), stomatitis (27.0%), dry skin (24.3%), nausea (23.6%), cough (20.9%), decreased appetite (20.3%), vomiting (14.9%), constipation (14.2%), headache (12.8%), anemia (12.2%), paronychia (11.5%), pyrexia (11.5%), dyspnea (10.8%), edema peripheral (10.8%), back pain (10.1%), and upper respiratory tract infection (10.1%)

One-hundred thirty-four (90.5%) patients experienced AEs of any grade that were suspected to be related to EGF816. The most frequent (>10% of patients) AEs of any CTCAE grade suspected to be related to EGF816 were rash (group term) (52%), diarrhea (36.5%), pruritus (33.8%), dry skin (24.3%), stomatitis (24.3%), fatigue (16.2%), nausea (15.5%), decreased appetite (12.2%), and vomiting (10.1%)

Seventy (47.3%) patients who were treated with EGF816 capsules or tablets at the dose levels specified below experienced Grade 3 or Grade 4 AEs regardless of relationship to the study drug. Grade 3/4 AEs occurring in  $\geq 2\%$  of patients were rash (grouped term) (15.5%), anemia (5.4%), pneumonia (5.4%), diarrhea (4.7%), fatigue (2.7%), dyspnea (2.7%), urticaria (2.7%), hypertension (2.7%), stomatitis (2.0%), decreased appetite (2.0%), hyperuricemia (2.0%), and seizure (2.0%).

Forty-four patients (29.7%) experienced Grade 3/4 AEs that were suspected to be related to EGF816. Those occurring in  $\geq 1\%$  of patients were rash (group term) (15.5%), anemia (2.7%), urticaria (2.7%), diarrhea (2.0%), fatigue (2.0%), stomatitis (2.0%), HBV (1.4%), and increased lipase (1.4%).

As of the data cutoff date (18-Dec-2015), SAEs, regardless of study drug relationship, were

Please refer to the current Investigator's Brochure for more details.

# 2.3 Gefitinib

Gefitinib is an oral first-generation EGFR inhibitor which reversibly inhibits the kinase activity of wild-type and certain activating mutations of EGFR, preventing autophosphorylation of tyrosine residues associated with the receptor, thereby inhibiting further downstream signaling and blocking EGFR-dependent proliferation. Gefitinib's binding affinity for EGFR exon 19 deletion or exon 21 point mutation L858R mutations is higher than its affinity for the wild-type EGFR. Gefitinib also inhibits IGF and PDGF-mediated signaling at clinically relevant concentrations; inhibition of other tyrosine kinase receptors has not been fully characterized.

Gefitinib is approved for the first-line treatment of EGFR-mutant NSCLC in the United States, Europe and Asia. The IPASS study was a randomized, multicenter, open-label trial conducted in patients with metastatic adenocarcinoma histology NSCLC receiving first-line treatment. Patients were randomized (1:1) to receive gefitinib 250 mg orally once daily or up to 6 cycles of carboplatin/paclitaxel. The efficacy outcomes included progression-free survival (PFS) and objective response rate (ORR) as assessed by BICR.

The subset population consisted of 186 of 1217 patients (15%) determined to be EGFR positive and had radiographic scans available for a retrospective assessment by BICR. In this subset, there were 88 gefitinib-treated patients and 98 carboplatin/paclitaxel-treated patients. Demographic and baseline characteristics of this subset were a median age of 59 years, age 75 years or older (7%), age less than 65 (70%), Asian (100%), female (83%), never smokers (96%), adenocarcinoma histology (100%), and PS 0-1 (94%).

The median duration of treatment for gefitinib-treated patients was 9.8 months. The hazard ratio for PFS favored the gefitinib-treated patients [HR of 0.54 (95% CI: 0.38, 0.79)] with a median PFS of 10.9 months for the gefitinib-treated patients and 7.4 months for the carboplatin/paclitaxel-treated patients as assessed by BICR. In addition, the objective response rate was 67% (95% CI: 56, 77) for gefitinib-treated patients and 41% (95% CI: 31, 51) for carboplatin/paclitaxel-treated patients based on BICR assessment. The median duration of response was 9.6 months for gefitinib-treated patients and 5.5 months for carboplatin/paclitaxel-treated patients.

Gefitinib is generally well-tolerated, with common side effects including rash and diarrhea. Rare but serious side effects including interstitial lung disease, hepatotoxicity and ocular disorders including keratitis can be seen.

[figure not shown]
Please see the gefitinib package insert and latest version of the investigator's brochure for further details.

A

# 2.4 Rationale for the combination of EGF816 and gefitinib

It is well-known that resistance to first generation EGFR inhibitors is mediated in a majority of cases by the development of a secondary mutation in EGFR exon 20, T790M. The development of T790M restores the receptor's affinity for ATP and prevents first-generation EGFR TKIs from effectively inhibiting EGFR^20. T790M

can be successfully overcome with thirdgeneration EGFR inhibitors, which bind covalently to EGFR and have activity

**Figure 1**. A WZ4002-resistant patient-derived cell line (121 Res) acquires a C797S mutation and maintains EGFR activity in the presence of TKI, while the parental (121 pt) cell line is sensitive to WZ4002.

against both T790M and the original founder EGFR mutations. We have now seen that resistance to third-generation EGFR TKIs is frequently mediated by the development of a tertiary resistance mutation in EGFR, C797S, which occurs at the site of covalent binding of all irreversible EGFR inhibitors. Indeed, using in vitro models, C797S renders cancers resistant to all tested third-generation EGFR inhibitors. Interestingly, cell lines bearing C797S alone, in the absence of T790M, retain sensitivity to first-generation EGFR inhibitors (erlotinib and gefitinib) which do not rely on C797 to engage in the drug pocket.

*In vitro* models suggest that the genetic context of the C797S mutation is important to its therapeutic implications. C797S which arises on the same allele (in *cis* configuration) with T790M renders the cells resistant to all currently available EGFR inhibitors; none are able to overcome the combination of both resistance mutations on the same DNA strand. However, in cell line models where T790M and C797S are on different alleles (in a *trans* configuration) retain sensitivity to combination of a first-generation and a third-generation EGFR inhibitor. This data suggests that upfront use of a combination of a 1st and 3rd generation EGFR inhibitor could not be overcome by development of either resistance mutation alone. Resistance to the combination would require the simultaneous development of C797S and T790M in a cis configuration, an event which is statistically unlikely. Thus, we hypothesize that the combination of a first and third-

generation EGFR inhibitor given together in the first-line setting may have the potential induce highly to durable remissions. the as of development both mutations in а cis configuration would be required to drive resistance. We therefore propose a phase II trial to test the efficacy and safety of EGF816 in combination with gefitinib for the first-line treatment of **EGFR-mutant NSCLC** 

[figure not shown]

Figure 2. EGFR C797S located in cis or trans with T790M alters drug sensitivity.

## 2.5 Correlative Studies Background

## 2.5.1 Pre-treatment, on-treatment and resistant tumor biopsies

Mandatory tumor biopsies will be required at the start of treatment and at the time of disease progression. These samples will be analyzed via next-generation sequencing at Novartis to characterize mechanisms of resistance to the EGF816/gefitinib combination.

In addition, an on-treatment biopsy will be obtained after about 2-3 weeks of treatment. These samples will allow for characterization of the response to treatment. Biopsies will be submitted for single-cell sorting and transcriptional profiling to study the direct effect of the TKI combination on tumor cells, and to identify potential early signs of eventual resistance to the combination. These exploratory analyses will be performed at Massachusetts General Hospital and at Novartis Pharmaceuticals.

## 2.5.2 Plasma-based circulating tumor DNA (ctDNA) analysis

The characterization of circulating tumor DNA (ctDNA) in patient plasma samples is now widely utilized on both a research and clinical basis. ctDNA has several advantages over tissue-based testing, and can serve as an key complement to traditional tumor biopsies. Tumor DNA is shed by cancer cells into the plasma from multiple disease sites; as our understanding of the intra and intertumoral heterogeneity which can exist within an individual patient grows, there is growing evidence that ctDNA can more fully capture the heterogeneity of disease present within the patient. In addition, ctDNA allows for easier sampling and facilitates longitudinal analyses

over time. We and others have demonstrated that longitudinal plasma assessments can be used to track response to treatment and that emerging resistance can be detected on the molecular level in the ctDNA prior to the development of radiographic disease progression.

In this study, longitudinal plasma samples will be obtained at the start of treatment, on D3, D8 and D15 of cycle 1,and at the start of each cycle and at the time of progression. Samples will be analyzed by ddPCR and next-generation sequencing to quantify molecular response to treatment, detect early signs of emerging resistant clones and to more fully characterize resistance mechanisms via NGS at the time of progression.

## **3.** PARTICIPANT SELECTION

## 3.1 Eligibility Criteria

Patients may be entered in the study only if they meet all of the following criteria:

- 3.1.1 Participants must have a pathologically-confirmed diagnosis of non-small cell lung cancer (NSCLC).
- 3.1.2 Participants must have advanced disease either stage IV disease, stage IIIB disease not amenable to definitive multi-modality therapy, or recurrent disease after a prior diagnosis of stage I-III disease. All staging is via the American Joint Committee on Cancer (AJCC)/IASLC 7th edition proposed staging criteria (see appendix 2)
- 3.1.3 An EGFR sensitizing mutation must be detected in tumor tissue. Specifically, patients harboring the most common mutations, deletions in exon 19 or the L858R mutation in exon 21 are eligible. Other EGFR sensitizing mutations may be eligible after discussion with the principal investigator. Patients may be enrolled in the study based on an activating EGFR mutation detected by a CLIA-certified tissue or plasma-based assay, but will be required to undergo a mandatory tumor biopsy during study screening.
- 3.1.4 Participants must have measurable disease, per RECIST 1.1. See Section 11 for the evaluation of measurable disease.
- 3.1.5 Patients in the six patient safety run-in cohort may have had a prior EGFR TKI in the metastatic setting (to allow for patients who started initial therapy at an outside hospital), but treatment duration must have been less than three months. After the initial six-patient safety run-in, no prior EGFR TKI therapy in the metastatic setting is allowed. An EGFR TKI given in the adjuvant setting (i.e. with no measurable disease at the time of administration) is allowable provided the subject has been off of EGFR TKI therapy for at least six months at the time of enrollment.

- 3.1.6 Patients may have had no more than one prior line of chemotherapy or immunotherapy in the metastatic setting. At least 14 days must have elapsed from the last chemo/immunotherapy administration until the start of protocol treatment, and patients must have recovered from the side effects of any of these agents.
- 3.1.7 Patients must be screened for HBV. Patients who are either HBsAg positive or HBV-DNA positive must be willing and able to take antiviral therapy 1-2 weeks prior to 1st dose of study treatment and continue on antiviral therapy for at least 4 weeks after the last dose of EGF816. Additional management of the patients would be provided by a physician with expertise in management of HBV, if needed. Patients must have negative hepatitis C antibody (HCV-Ab) or positive HCV-Ab but undetectable level of HCV-RNA. Note: patients with detectable HCV-RNA are not eligible for the study.
- 3.1.8 Patients must receive insurance approval for or be willing to pay for commercial gefitinib.
- 3.1.9 Age  $\geq$  18 years.
- 3.1.10 ECOG performance status  $\leq 2$  (Karnofsky  $\geq 60\%$ , see Appendix A)
- 3.1.11 Life expectancy of greater than 12 weeks.
- 3.1.12 Participants must have normal organ and marrow function as defined below:
  - Leukocytes  $\geq$ 3,000/mcL
  - Absolute neutrophil count  $\geq$ 1,500/mcL
  - Platelets  $\geq 100,000$ /mcL
  - Total bilirubin <1.5 x upper limit of normal (ULN) \**For patients with Gilbert's syndrome total bilirubin* <3.0 x ULN
    - AST(SGOT)/ALT(SGPT) ≤3 × institutional upper limit of normal; for patients with known hepatic metastases AST and/or ALT > 5x ULN
    - Creatinine  $\leq 1.5 \times$  institutional upper limit of normal
- 3.1.13 The effects of EGF816 and gefitinib on the developing human fetus are unknown. For this reason, women of child-bearing potential and men must agree to use highly effective contraception during the study and for 3 months after stopping the study treatment. Highly effective contraception methods include:
  - Total abstinence (when this is in line with the preferred and usual lifestyle of the subject. Periodic abstinence (e.g., calendar, ovulation, symptomthermal, postovulation methods) and withdrawal are not acceptable methods of contraception
  - Female sterilization (have had surgical bilateral oophorectomy with or without hysterectomy) or tubal ligation at least six weeks before taking study treatment. In case of oophorectomy alone, only when the reproductive status of the woman has been confirmed by follow up hormone level assessment

- Male Partner: male sterilization (at least 6 months prior to screening). For female subjects on the study the vasectomized male partner should be the sole partner for that subject.
- **Combination** of any **two** of the following (a+b or a+c, or b+c):
  - A. Use of oral, injected or implanted hormonal methods of contraception or other forms of hormonal contraception that have comparable efficacy (failure rate <1%), for example hormone vaginal ring or transdermal hormone contraception.
  - B. Placement of an intrauterine device (IUD) or intrauterine system (IUS)
  - C. Barrier methods of contraception: Condom or Occlusive cap (diaphragm or cervical/vault caps) with spermicidal foam/gel/film/cream/vaginal suppository.
  - D. In case of use of oral contraception women should have been stable on the same pill for a minimum of 30 days before taking study treatment.
  - Women are considered post-menopausal and not of childbearing potential if they have had 12 months of natural (spontaneous) amenorrhea with an appropriate clinical profile (e.g. age appropriate, history of vasomotor symptoms) or have had surgical bilateral oophorectomy (with or without hysterectomy) or tubal ligation at least six weeks ago. In the case of oophorectomy alone, only when the reproductive status of the woman has been confirmed by follow up hormone level assessment is she considered not of childbearing potential.
- Sexually active males must agree to use a condom during intercourse while taking drug and for 3 months after stopping treatment; men should not father a child in this period. A condom is required to be used also by vasectomized men in order to prevent delivery of the drug via seminal fluid.
- 3.1.14 Ability to understand and the willingness to sign a written informed consent document. Written informed consent must be obtained prior to any screening procedures.

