## 4. **REGISTRATION PROCEDURES**

## 4.1 General Guidelines for DF/HCC Institutions

Institutions will register eligible participants in the Clinical Trials Management System (CTMS) OnCore. Registrations must occur prior to the initiation of protocol therapy. Any participant not registered to the protocol before protocol therapy begins will be considered ineligible and registration will be denied.

An investigator will confirm eligibility criteria and a member of the study team will complete the protocol-specific eligibility checklist.

Following registration, participants may begin protocol therapy. Issues that would cause treatment delays should be discussed with the Overall Principal Investigator (PI). If a participant does not receive protocol therapy following registration, the participant's registration on the study must be canceled. Registration cancellations must be made in OnCore as soon as possible.

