- Certification that patient meets all inclusion and exclusion criteria and is able to comply with all requirements of the clinical trial
- Review concomitant medications since screening
- Perform physical examination with vital signs and ECOG performance status
- Blood investigations to be done if screening labs were done more than 7 days prior to day 1.
- Blood investigations performed on C1D1 must be reviewed before starting treatment to ensure that there are no clinically significant abnormalities. However, C1D1 laboratory studies do not have to re-meet eligibility criteria to begin treatment.
- Blood for correlative ctDNA analyses

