# 6.1.2 Management of liver function abnormalities (bilirubin, AST, ALT)

# Table 6-4: Guidelines for management of abnormal LFTs: Investigations (Henatic)a

Investigations (Hepatic) a		
Total Bilirubin (for patients with Gilbert Syndrome these dose modifications apply to changes in		
direct [conjugated] bilirubin only)		
Grade 1 (>ULN and $\leq 1.5 \times ULN$ )	Maintain dose level with liver function test	
	(LFTs) monitored as per protocol	
Grade 2 (>1.5 and $\leq$ 3.0 x ULN) with ALT or	Omit both drugs until resolved to $\leq$ grade 1, then:	
$AST \leq 3.0 x ULN$	If resolved in $\leq$ 7 days, then resume EGF816 at	
	the original dose level with close LFT	
	monitoring. Resume gefitinib at the original dose	
	level if LFTs remain < g rade 1 after 7 days of	
	EGF816.	
	If resolved in $>7$ days, then resume drugs one at a	

	time (as above) with one level dose reduction in each drug.
Grade 3 (>3.0 and ≤10.0 x ULN) with ALT or AST ≤3.0 x ULN	Omit both drugs until resolved to $\leq$ grade 1, then: If resolved in $\leq$ 7 days, resume EGF816 with one level dose reduction and close LFT monitoring. Resume gefitinib with one level dose reduction if LFTs remain $\leq$ grade 1 after 7 days of EGF816. If resolved in $\Box$ 7 days discontinue patient from study treatment.
	The patient should be monitored weekly (including LFTs b ), or more frequently if clinically indicated, until total bilirubin has resolved to baseline or stabilized over 4 weeks.
Grade 4 (>10.0 x ULN)	Permanently discontinue study treatment. The patient should be monitored weekly (including LFTs), or more frequently if clinically indicated, until total bilirubin has resolved to baseline or stabilized over 4 weeks.
AST or ALT	
Grade 1 (>ULN and $\leq 3.0 \text{ x ULN}$ )	Maintain dose level with LFTs monitored per protocol
Grade 2 (>3.0 and ≤5.0 x ULN) without total bilirubin elevation to >2.0 x ULN	Maintain dose level with LFTs monitored per protocol
Grade 3 (>5.0 and ≤20.0 x ULN) without total bilirubin elevation to >2.0 x ULN	Omit both drugs until resolved to $\leq$ Grade 1 (or to baseline), then resume EGF816 with one level dose reduction and close LFT monitoring. Resume gefitinib with one level dose reduction if LFTs remain $\leq$ grade 1 after 7 days of EGF816. Permanently discontinue study treatment if $\geq$ Grade 3 elevation recurs.

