	If AST or ALT > 5 x ULN in patients with baseline AST or ALT $\leq$ 3 x ULN, or if AST or ALT > 8 x ULN in patients with baseline AST or ALT > 3 x ULN but $\leq$ 5 x ULN, immediate testing for viral hepatitis infection or reactivation should be performed , see Section 6.1.3. Patients who have HBV-DNA monitoring during the study should be an tested immediately
Grade 4 (>20.0 x ULN) without total bilirubin elevation to >2.0 x ULN	during the study should be re-tested immediately.Omit both drugs until resolved to ≤ Grade 1 (or to baseline), then resume EGF816 with one level dose reduction and close LFT monitoring.Resume gefitinib with one level dose reduction if

LFTs remain $\leq$ grade 1 after 7 days of EGF816.
However, permanently discontinue study
treatment if the elevation of Grade 4 recurs.
If AST or ALT>20.0 x ULN immediate testing
for viral hepatitis infection or reactivation
should be performed, see Section 6.1.3. Patients
who have HBV-DNA monitoring during the
study should be retested immediately.

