## On study monitoring of liver function test (LFT) for all patients

LFTs should be monitored for all patients as per protocol, or more frequently if clinically indicated.

At any time during the study, if  $ALT > 5 \times ULN$  in patients with baseline  $ALT \le 3 \times ULN$ , or if  $ALT > 8 \times ULN$  in patients with baseline  $ALT > 3 \times ULN$  but  $\le 5 \times ULN$ : immediately

- 1. Perform test(s) for viral hepatitis infection or reactivation: all patients should be screened with viral hepatitis panel (HAV-Ab-IgM, HBsAg, HBcAb-IgM, and HCV-Ab). In addition:
  - a. Patients who have HBV-DNA monitoring during the study should be re-tested for HBV-DNA immediately; refer to Table 6-6 for definition and management of HBV reactivation.
  - b. Patients who have HCV-RNA monitoring during the study should be re-tested for HCV-RNA immediately; refer to Table 6-7 for definition and management of HCV reactivation.
- 2. If any of the above tests indicate:
  - a. HBV reactivation: refer to Table 6-6 for management guidelines.
  - b. HCV reactivation: refer to Table 6-7 for management guidelines.
  - c. New viral infection: immediately interrupt EGF816 and gefitinib dosing, consult a physician with expertise in managing viral hepatitis and contact study PI for further discussion.
- 3. Perform other relevant tests/procedures as clinically indicated.
- 4. Follow the dosing modification for ALT elevation according to guidelines in Table 6-4.

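### Section 3.1.12 reverses the AST/ALT limit for liver metastases: it requires values above 5 × ULN where the rest of the protocol implies at most 5 × ULN

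*Combined protocol and SAP*

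**What the plan says.** Section 3.1 admits only patients who meet every listed criterion. Item 3.1.12 opens with "Participants must have normal organ and marrow function as defined below". It caps AST and ALT at 3 × ULN and continues with "for patients with known hepatic metastases AST and/or ALT > 5x ULN". The exclusion criteria in Section 3.2 give no AST or ALT limit.

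The hepatic management rules assume something different. Table 6-4 (Section 6.1.2) has a row headed "Grade 3 (>5.0 and ≤20.0 x ULN) without total bilirubin elevation to >2.0 x ULN", under which both drugs are held. That row calls for immediate viral hepatitis testing above 5 × ULN when baseline is at most 3 × ULN. For the next baseline band the trigger is "ALT > 8 x ULN in patients with baseline AST or ALT > 3 x ULN but" no more than 5 × ULN. The Grade 4 row gives a trigger that does not depend on baseline: "If AST or ALT>20.0 x ULN immediate testing".

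Section 6.1.3, under on-study monitoring of liver function, uses the same two baseline bands for ALT only and attaches the instruction "Perform test(s) for viral hepatitis infection or reactivation".

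Section 5.2.1 has any Cycle 1 Day 1 bloods reviewed for clinically significant abnormalities, but "C1D1 laboratory studies do not have to re-meet eligibility criteria to begin treatment". Under Section 4.1 an investigator confirms eligibility and staff "complete the protocol-specific eligibility checklist"; the checklist is not in the documents.

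**The concern.** A relaxed liver-enzyme limit for patients with liver metastases should be a higher ceiling. Here it is a floor with nothing above it. Followed literally, it refuses the patients whom the protocol's own monitoring bands describe and admits patients with Grade 3 or Grade 4 values, for whom those bands say nothing.

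This is a working safety threshold. Section 2.3 names hepatotoxicity among gefitinib's rare but serious effects. Section 2.2.2 reports a death from hepatitis B reactivation considered related to EGF816. The hepatitis-testing triggers therefore guard against a harm already seen with the study drug, and they have a gap for the patients this clause lets in.

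A site that silently corrects the sign does not solve the problem. It would enrol patients at >3 to ≤5 × ULN who fail the written criterion, and each would be an eligibility deviation.

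**Working it through.** No statistical figure is involved. The check compares thresholds interval by interval, for an isolated AST/ALT elevation in a patient with known liver metastases. Let *x* be the screening value in multiples of ULN.

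**Inputs**

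- Section 3.1.12: general limit *x* ≤ 3; liver-metastasis clause *x* > 5.
- Section 3.2: no AST/ALT limit.
- Table 6-4 grades: Grade 2 is >3.0 to ≤5.0, Grade 3 is >5.0 to ≤20.0, Grade 4 is >20.0.
- Hepatitis-testing triggers (Table 6-4 for AST or ALT; Section 6.1.3 for ALT): >5 if baseline ≤3; >8 if baseline >3 to ≤5. The Grade 4 row of Table 6-4 adds >20 at any baseline.

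**Step 1: who is eligible as written**

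- Clause replaces the general limit: eligible if *x* > 5. Even normal values are excluded.
- Clause is an alternative to the general limit: eligible if *x* ≤ 3 or *x* > 5.
- Common to both readings: 3 < *x* ≤ 5 is excluded, and *x* > 5 is admitted without an upper bound.

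**Step 2: eligibility against the monitoring rules**

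| Baseline (× ULN) | Clause replaces limit | Clause is alternative | Corrected to ≤5 | Testing trigger |
|---|---|---|---|---|
| ≤3 | not eligible | eligible | eligible | >5 |
| >3 to ≤5 | not eligible | not eligible | eligible | >8 |
| >5 to ≤20 | eligible | eligible | not eligible | none specific to baseline; next is >20 |
| >20 | eligible | eligible | not eligible | already above >20 at entry |

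**Step 3: whom the >8 × ULN rule serves**

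Without liver metastases, eligibility stops at 3 × ULN. With them, the band from >3 to ≤5 is excluded on both readings. So no patient qualifies at screening with a value in that band. If the clause reads ≤5, the band holds exactly the patients for whom the limit was relaxed, and the highest admissible value, 5 × ULN, equals the top of the band.

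One qualification: Cycle 1 Day 1 values need not re-meet eligibility, so a patient could qualify at ≤3 and drift into the band before dosing. Drift does not explain why the band ends at 5, because drift could pass 5 and the tables make no provision for that. An entry limit of 5 × ULN does explain it.

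**The case against.** The strongest reply is that this is an obvious slip which few investigators would follow. A criterion for normal organ function that demands enzymes above 5 × ULN makes no clinical sense, and a site could infer the intended limit from Table 6-4, as is done here. Other protections remain: the bilirubin entry cap (<1.5 × ULN, or <3.0 × ULN in Gilbert's syndrome), hepatitis B and C screening, the combined enzyme-and-bilirubin rule, and the review of Cycle 1 Day 1 bloods. These make admission at very high values unlikely in practice. But none of them caps isolated AST/ALT, and the blood review has no numeric limit.

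Three further points narrow the argument:

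- **Dose holds.** The general dose rules in Section 6 concern toxicity possibly related to study drug, and the Grade 3 row allows resumption on return to baseline. A patient who enters at 6 × ULN because of liver metastases is not clearly subject to a hold. Conflict with the hold rule is therefore weaker evidence than the mismatch with the baseline bands, and the conclusion does not depend on it.
- **Fold rises.** From 4 to 8 is 8/4 = 2.0-fold and from 6 to 20 is 20/6 = 3.3-fold, which looks less protective. But from 2 to 5 is 5/2 = 2.5-fold and from 8 to 20 is 20/8 = 2.5-fold. The comparison depends on the starting value and shows no harm by itself.
- **A conversion error.** Some comparison signs elsewhere in the extracted text are damaged, so a misread sign cannot be fully ruled out. The visible damage is boxes or a lost underline rather than a reversed sign, and the ≤ before 3 × in the same item is intact.

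These points trim the supporting argument. They leave the reversed limit and its correction untouched.

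**Conclusion.** The concern holds. As written, Section 3.1.12 excludes patients with liver metastases at >3 to ≤5 × ULN and admits those above 5 × ULN without limit, on either reading of the clause. If the clause replaces the general limit, it also excludes those at ≤3 × ULN. The protocol contradicts itself, and the baseline bands in Table 6-4 and Section 6.1.3 point to ≤5 × ULN as the intended limit.

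The number of patients affected cannot be derived from the documents, which also do not show that anyone was enrolled under the literal reading. The conclusion assumes that the sign in the extracted text matches the source and that baseline means the screening value used for eligibility. This is a drafting error in a safety criterion, not a flaw in the statistical design. It must be fixed because sites confirm eligibility against this text.

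**What to change.** Amend Section 3.1.12 so that the limit for known hepatic metastases is ≤ 5 × ULN, after confirming the sign in the source document. It would also help to state that both AST and ALT must meet the limit, since and/or is ambiguous once the limit is a ceiling. Check that the protocol-specific eligibility checklist carries the same limit. Review baseline AST/ALT for every enrolled patient with liver metastases against the corrected limit.

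The cost is a one-symbol amendment, a checklist check and a short data review. The two-stage design, the sample size of 36 and the analysis do not change.
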